## 1.0 TRIAL SUMMARY

[figure not shown]
Abbreviated Title	Pembrolizumab for MRD in Adults with ALL
Trial Phase	II
Clinical Indication	Acute lymphoblastic leukemia/lymphoma
Trial Type	Single-arm, non-randomized
Type of control	None
Route of administration	Intravenous
Trial Blinding	None
Treatment Groups	1
Number of trial subjects	21
Estimated enrollment period	6/1/2016 – 10/1/2018
Estimated duration of trial	3 years
Duration of Participation	Up to 2 years

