### 5.1.3 Subject Exclusion Criteria

The subject must be excluded from participating in the trial if the subject:

1. Is currently participating and receiving study therapy or has participated in a study of an investigational new drug and received study therapy or used an investigational device within 4 weeks of the first dose of treatment.
2. Has a diagnosis of immunodeficiency or is receiving systemic steroid therapy or any other form of immunosuppressive therapy within 7 days prior to the first dose of trial treatment.
3. Has a known history of active TB (Bacillus Tuberculosis).
4. Has a known hypersensitivity to pembrolizumab or any of its excipients.
5. Has had a prior anti-cancer monoclonal antibody (mAb) within 4 weeks prior to study Day 1 or who has not recovered (i.e.,  $\leq$  Grade 1 or at baseline) from adverse events due to agents administered more than 4 weeks earlier.
6. Has had prior chemotherapy, targeted small molecule therapy, or radiation therapy within 2 weeks prior to study Day 1 or who has not recovered (i.e.,  $\leq$  Grade 1 or at baseline) from adverse events due to a previously administered agent.
  - Note: Subjects with  $\leq$  Grade 2 neuropathy or with hematologic toxicity that has recovered to levels above that stated in Inclusion Criterion 6 are an exception to this criterion and may qualify for the study if all other inclusion/exclusion criteria are met.
  - Note: If subject received major surgery, they must have recovered adequately from the toxicity and/or complications from the intervention (i.e.,  $\leq$  Grade 1 or at baseline) prior to starting therapy.
7. Has a known additional malignancy that is progressing or requires active treatment. Exceptions include basal cell carcinoma of the skin or squamous cell carcinoma of the skin that has undergone potentially curative therapy or in situ cervical cancer.
8. Has known active central nervous system (CNS) leukemia and/or leukemic meningitis. Subjects with previously treated CNS leukemia may participate provided they are stable (e.g., without evidence of active disease by imaging for at least four weeks prior to the first

9458- Protocol Version Date 28 Feb 2019

dose of trial treatment and any neurologic symptoms have returned to baseline) and have no evidence of leukemic blasts on analysis of cerebrospinal fluid (CSF).

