## 5.8 Subject Withdrawal/Discontinuation Criteria

Subjects may withdraw consent at any time for any reason or be dropped from the trial at the discretion of the investigator should any untoward effect occur. In addition, a subject may be withdrawn by the treating investigator or the PI if enrollment into the trial is inappropriate, the trial plan is violated, or for administrative and/or other safety reasons. Specific details regarding discontinuation or withdrawal are provided in Section 7.1.4 – Other Procedures.

A subject must be discontinued from the trial for any of the following reasons:

- The subject or legal representative (such as a parent or legal guardian) withdraws consent.
- Confirmed morphologic relapse/progression
- Radiologic studies highly suspicious for extramedullary relapse (biopsy confirmation is strongly recommended unless prohibitively risky or patient refuses)
- Unacceptable adverse experiences as described in Section 5.2.1.2
- Intercurrent illness that prevents further administration of treatment
- Treating investigator feels that alternative treatment (e.g., allogeneic HCT) would be more beneficial for the subject
- Investigator's decision to withdraw the subject
- The subject has a confirmed positive serum pregnancy test
- Noncompliance with trial treatment or procedure requirements
- The subject is lost to follow-up
- Completed 24 months of uninterrupted treatment with pembrolizumab or 35 administrations of study medication, whichever is later.

*Note: 24 months of study medication is calculated from the date of first dose. Subjects who stop pembrolizumab after 24 months may be eligible for up to one year of additional study treatment if they progress after stopping study treatment provided they meet the requirements detailed in Section 7.1.5.5*

- Administrative reasons

The End of Treatment and Follow-up visit procedures are listed in Section 6 (Protocol Flow Chart) and Section 7.1.5 (Visit Requirements). After the end of treatment, each subject will be followed for 30 days for adverse event monitoring (serious adverse events will be collected for 90 days after the end of treatment as described in Section 7.2.3.1). Subjects who discontinue for reasons other than progressive disease will have post-treatment follow-up for

9458- Protocol Version Date 28 Feb 2019

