### **5.9 Subject Replacement Strategy**

Subjects will be replaced only in the rare event that they are not evaluable, which will be defined as alive > 3 weeks after initiation of study treatment but without sufficient response data from bone marrow examination (refused response assessments, technical limitations precluding ability to review bone marrow status, etc.).

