For subjects who are eligible to proceed to Cycles 3 and beyond, bone marrow exams will be repeated after every other cycle (i.e., Cycle 4, 6, and 8) through Cycle 8. For those eligible to continue beyond Cycle 8, the timing of subsequent bone marrow exams will be left to the treating investigator, though every 3 months while receiving study treatment will be recommended.

A bone marrow exam will also be required at the end of treatment. If the decision to discontinue treatment coincides with the timing of one of the above follow-up assessments, a separate end-of-treatment examination will not be required (e.g., the post-cycle 4 bone marrow demonstrated morphologic relapse). Similarly, if morphologic relapse is detected after Cycle 1, no further bone marrow examinations will be required for this study.

For definitions of response categories, please see Section 12.3.

Imaging studies will only be performed if extramedullary disease is suspected based on the evaluation of the treating investigator. This may occur at screening (to ensure eligibility) or at end of treatment (to document relapse/progression). If extramedullary disease is identified, this will constitute disease relapse: study treatment will be discontinued, and the subject will be removed from the study.

9458- Protocol Version Date 28 Feb 2019

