### 9.2 Statistical Analysis Plan

The primary endpoint of this phase II study will be the rate of complete MRD response, defined as the percentage of evaluable subjects who achieve a complete MRD response, as defined in Section 11.3. The study of blinatumomab for chemorefractory MRD cited previously assumed an historical rate of complete MRD response to standard chemotherapy of 5%. Considering the fact that the current study will enroll patients that have previously received or are ineligible for treatment with blinatumomab, we feel it is reasonable to assume a similar historical rate of complete MRD response for subjects in this trial. The design will be based on Simon's two-stage minimax design with an historical response rate of 5% and an assumed-true response rate of 20% for patients receiving treatment on this protocol. The design also assumed a 10% type-I error rate and a 20% type-II error rate. Under these assumptions and parameters, the first stage will enroll 12 evaluable patients. If 0 responses are seen among these 12, the study will be paused for futility to consider alternative strategies to improve efficacy versus consideration of study closure (the probability of 0 responses among 12 under the alternative hypothesis of 20% response is 0.07). On the other hand, if at least 1 response is seen among the first 12 patients, an additional 9 will be enrolled for a total of 21. If at least 3 responses occur among the 21 (14.3% or more), this will be considered as sufficient evidence to conclude that the observed response rate is statistically better than the fixed historical rate of 5%. This yields a type-I error rate of .08 and power of 80% along with an expected sample size of 16.1.

Additionally, the study will be stopped early if there is a signal of unacceptably-high early morphologic relapse. For this stopping rule, the rate of morphologic relapse within the first 2 cycles of treatment will be assessed in cohorts of 5 for the first 15 patients enrolled. If the lower bound of the 80% confidence

interval of the morphologic relapse rate exceeds 50% at these assessments (i.e.,  $\geq 4$  out of 5,  $\geq 7$  out of 10, and  $\geq 10$  out of 15), the study will close early.

Reporting of secondary endpoints, including toxicity profiles, OS, and impact of biomarkers, will be primarily descriptive.

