**12.3 Response Evaluation Criteria**

Consensus guidelines regarding definitions of MRD were developed following the Second International Symposium on MRD Assessment. To summarize, quantifiable MRD is required for eligibility for this study. Complete MRD response is defined as having achieved MRD negativity or no longer detectable. MRD persistence is defined as continuously quantifiable MRD positivity measurable at  $\geq 2$  time points with  $\geq 1$  relevant treatment element (e.g., a cycle of study treatment) in between. MRD reappearance is

conversion from MRD negativity to quantifiable MRD positivity. Low-level, non-quantifiable MRD positivity does not fit into any of these categories.

For the purposes of determining morphologic relapse/progression, this will be defined as the appearance of leukemic blasts in the peripheral blood or  $\geq 5\%$  blasts in the bone marrow not attributable to any other cause.

When considering subject eligibility or signs of treatment failure, extramedullary disease will be suspected in the presence of lymph nodes  $> 1.5$  cm in longest diameter, extranodal sites  $> 1.0$  cm in longest diameter, or splenomegaly with an increase in length of  $> 50\%$ . These definitions are adapted from international working group criteria for the evaluation of lymphoma (the Lugano classification). For the purposes of this study, these parameters will not define the presence of extramedullary disease, but instead will be used as a guide to consider its presence; when feasible and if the results of imaging studies are equivocal, biopsy will be preferred to confirm or refute this suspicion.

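### The early-relapse closure rule in Section 9.2 counts blood and marrow relapse only, so an isolated extramedullary relapse in the first two cycles enters the count as a non-event

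*Combined protocol and SAP*

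**What the plan says.** Section 9.2 states that "the study will be stopped early if there is a signal of unacceptably-high early morphologic relapse". The looks are specified as follows: "the rate of morphologic relapse within the first 2 cycles of treatment will be assessed in cohorts of 5 for the first 15 patients enrolled". The condition is that the lower bound of an 80% confidence interval exceeds 50%, printed as at least 4 of 5, 7 of 10 and 10 of 15. The study then closes. This is firmer than the response futility look at 12 evaluable patients, which only pauses the study.

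The counted event is defined in Section 12.3: "For the purposes of determining morphologic relapse/progression, this will be defined as the appearance of leukemic blasts in the peripheral blood", or at least 5% marrow blasts with no other cause. Section 7.1.2.6 gives the same definition. Neither mentions extramedullary disease.

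Extramedullary disease is handled separately. Section 7.1.2.6 says: "If extramedullary disease is identified, this will constitute disease relapse"; treatment then stops and the patient leaves the study. Section 5.8 has its own discontinuation item, "Radiologic studies highly suspicious for extramedullary relapse", beside the item for confirmed morphologic relapse. The note to the diagram in Section 2.2 also names the two events separately.

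**The concern.** The protocol recognises two kinds of frank relapse with the same consequence for the patient, and the closure rule counts one of them. A patient with an isolated extramedullary relapse in cycle 1 or 2 (no blood blasts, marrow blasts below 5%) remains one of the first 5, 10 or 15 enrolled without adding to the relapse count. In the arithmetic of the rule, that patient is indistinguishable from one who has not relapsed.

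This is the only numerical rule that closes the trial for early relapse; the termination criteria in Section 5.10 contain none. With looks at 5, 10 and 15 patients, a single uncounted relapse can decide the outcome. The omission works in one direction only: it can delay or prevent closure, never cause it. The response boundaries are not involved, and closing early cannot raise the type I error of the response test.

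**Working it through.** **1. Reproduce the printed counts.** Inputs from Section 9.2: 80% interval, 50% threshold, n = 5, 10, 15. The interval method is not stated. The two-sided 80% Wald lower limit is L = x/n − 1.2816·√[(x/n)(1 − x/n)/n].

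- 4/5: 0.800 − 1.2816·√(0.16/5) = 0.571; 3/5 gives 0.319.
- 7/10: 0.514; 6/10 gives 0.401.
- 10/15: 0.511; 9/15 gives 0.438.

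Each printed count is the smallest that clears 50%. A one-sided 80% exact limit gives the same counts (0.510, 0.516, 0.524). A two-sided 80% exact limit does not (0.416, 0.448, 0.468). The printed counts are therefore sound, and the point concerns only which event enters them.

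**2. One-patient cases, with no assumed rate.**

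| Look | Blood/marrow + extramedullary only | Counted under 9.2 (L) | Disease relapse per 7.1.2.6 (L) |
|---|---|---|---|
| 5 | 3 + 1 | 3/5 (0.319), continue | 4/5 (0.571), close |
| 10 | 6 + 1 | 6/10 (0.401), continue | 7/10 (0.514), close |
| 15 | 9 + 1 | 9/15 (0.438), continue | 10/15 (0.511), close |

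Dropping the patient from the denominator would not restore closure: 3/4, 6/9 and 9/14 give Wald limits of 0.473, 0.465 and 0.479.

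**3. Average effect under assumed rates.** Let r be the true early disease-relapse rate and e the share of those relapses that are extramedullary only. The documents give neither. The rate that the rule sees is p = r(1 − e). With X5, X10 and X15 the cumulative counts,

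P(close) = P(X5 ≥ 4) + P(X5 ≤ 3, X10 ≥ 7) + P(X5 ≤ 3, X10 ≤ 6, X15 ≥ 10),

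computed from exact binomial probabilities, with independent patients and two-cycle status complete at each look.

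- r = 0.60, e = 0, p = 0.60: the first term is 5(0.6⁴)(0.4) + 0.6⁵ = 0.337; adding 0.134 and 0.076 gives 0.548.
- r = 0.60, e = 0.10, p = 0.54: 0.242 + 0.094 + 0.051 = 0.386 (terms rounded).

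| r | All relapses count | e = 1% | 2% | 5% | 10% | 20% |
|---|---|---|---|---|---|---|
| 60% | 54.8% | 53.1% | 51.4% | 46.5% | 38.6% | 24.9% |
| 70% | 80.7% | 79.1% | 77.5% | 72.4% | 63.1% | 43.8% |

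**4. The same formula below the threshold.** If all relapses count, closure is 3.7% at r = 30% and 12.0% at r = 40%. At e = 20% the rule as written sees p = 0.24 and 0.32, and closes with probability 1.5% and 4.8%.

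**The case against.** **The event is defined.** A reader might infer that the sections contradict each other, or that the rule is ambiguous. The documents do not support that. Morphologic relapse is defined twice in the same terms, and extramedullary disease is called disease relapse, never morphologic relapse. What stands is narrower: a clearly defined event leaves out one kind of relapse that the protocol itself recognises.

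**A blood-and-marrow event has a rationale.** Marrow is examined after cycles 1 and 2, matching the window of the rule, and blood counts are taken every cycle. Imaging is done only on suspicion, and Section 12.3 uses its size criteria as a guide rather than a definition. Adding extramedullary relapse brings a judgement-dependent event into a firm count. This is a real cost, but Section 7.1.2.6 already relies on the same judgement to remove the patient.

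**The event may be uncommon.** Entry requires no clinically apparent extramedullary disease, and active CNS leukemia is excluded. "Subjects with previously treated CNS leukemia may participate provided they are stable", but they must also have no blasts in the cerebrospinal fluid. The summary gives the indication as "Acute lymphoblastic leukemia/lymphoma", while Section 5.1.1 requires ALL. These passages show that isolated extramedullary relapse within about six weeks is possible. They do not show that it is frequent, so a reader should not infer a large loss: at shares of 1% or 2% the loss at 60% is 1.7 or 3.3 percentage points.

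**Other oversight exists.** Under Section 8.0 the committees review the study at least annually and as needed, and can act outside the rule. That limits the consequence but does not change what the rule counts.

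**The denominator.** A reader might also infer that using enrolled rather than evaluable patients sets the interval against the printed counts. With 6 relapses among 8 assessed of 10 enrolled, the Wald limit for 6/8 is 0.554, yet 6/10 misses the count of 7. This depends on an interval method that the plan does not state (the two-sided exact limit is 0.462) and on denominators at which the rule does not look. Blood blasts alone establish morphologic relapse, so missing marrow need not mean unknown status. Section 5.9 also expects few such patients: "Subjects will be replaced only in the rare event that they are not evaluable". It is a minor, optional clarification and not part of this point.

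**Conclusion.** The point holds as a cheap improvement to a patient-protection rule. It does not show an arithmetic error or a contradiction. Under the definitions in force, an isolated extramedullary relapse in the first two cycles is a non-event for closure, and one such patient can keep the trial open at any of the three looks. That follows from the text alone.

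The average effect cannot be fixed from the documents. At a true early relapse rate of 60%, it runs from about 2 percentage points of closure probability at a 1% extramedullary-only share to about 30 points at 20%. These figures rest on assumed rates, independent patients and complete status at each look. A patient who also has blood blasts or at least 5% marrow blasts is already counted, and the printed counts and the response design are unaffected.

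**What to change.** In Section 9.2, make the counted event *morphologic relapse per Section 12.3 or extramedullary relapse per Section 7.1.2.6, within the first 2 cycles of treatment*. Use this wording wherever the rule now refers to morphologic relapse alone, and keep the counts of 4/5, 7/10 and 10/15. Nothing changes in the assessments, the sample size or the handling of individual patients.

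There are two costs. The count then includes an event found only when it is clinically suspected, so each one counted should be documented for the monitoring committee. Closure also becomes more likely wherever extramedullary relapse occurs, including at true rates below 50%: at an assumed 20% share it rises from 4.8% to 12.0% at a 40% relapse rate, and from 1.5% to 3.7% at 30%. At smaller shares the rise is smaller.

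Optionally, one further sentence could say how an enrolled patient with unknown relapse status through cycle 2 enters the count.

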## 10.0 LABELING, PACKAGING, STORAGE AND RETURN OF CLINICAL SUPPLIES

### 10.1 Investigational Product

The investigator shall take responsibility for and shall take all steps to maintain appropriate records and ensure appropriate supply, storage, handling, distribution and usage of investigational product in accordance with the protocol and any applicable laws and regulations.

Clinical Supplies will be provided by Merck as summarized in Table 7.

Table 7: Product Descriptions

Product Name & Potency	Dosage Form
Pembrolizumab 50 mg	Lyophilized Powder for Injection
Pembrolizumab 100 mg/ 4mL	Solution for Injection

### 10.2 Packaging and Labeling Information

Clinical supplies will be affixed with a clinical label in accordance with regulatory requirements.

### 10.3 Clinical Supplies Disclosure

This trial is open-label; therefore, the subject, the trial site personnel, the Sponsor and/or designee are not blinded to treatment. Drug identity (name, strength) is included in the label text; random code/disclosure envelopes or lists are not provided.

### 10.4 Storage and Handling Requirements

Clinical supplies must be stored in a secure, limited-access location under the storage conditions specified on the label.

Receipt and dispensing of trial medication must be recorded by an authorized person at the trial site.

Clinical supplies may not be used for any purpose other than that stated in the protocol.

### 10.5 Returns and Reconciliation

The investigator is responsible for keeping accurate records of the clinical supplies received from Merck or designee, the amount dispensed to and returned by the subjects and the amount remaining at the conclusion of the trial.

Upon completion or termination of the study, all unused and/or partially used investigational product will be destroyed at the site per institutional policy. It is the Investigator's responsibility to arrange for

disposal of all empty containers, provided that procedures for proper disposal have been established according to applicable federal, state, local and institutional guidelines and procedures, and provided that appropriate records of disposal are kept.

## **11.0 ADMINISTRATIVE AND REGULATORY DETAILS**

### **11.1 Confidentiality**

The investigator will assure that subjects' anonymity will be strictly maintained and that their identities are protected from unauthorized parties. Only subject initials, date of birth and a study identification code will be recorded on any form or biological sample submitted to Merck or applicable outside institutions/laboratories. Laboratory specimens will be labeled in such a way as to protect subject identity while allowing the results to be recorded to the proper subject. The investigator will keep a screening log showing study identification codes, names, date of birth and last known address for all subjects screened and for all subjects enrolled in the trial. Subject data will be processed in accordance with all applicable regulations.

### **11.2 Compliance with Financial Disclosure Requirements**

The investigator and all applicable subinvestigators will comply with 21 CFR, Part 54, 1998, providing documentation of their financial interest or arrangements with Merck, or proprietary interests in the investigational drug under study. This documentation will be provided prior to the investigator's (and any subinvestigator's) participation in the study. The investigator and subinvestigator will notify applicable parties of any change in reportable interests during the study.

### **11.3 Compliance with Trial Registration and Results Posting Requirements**

Under the terms of the Food and Drug Administration Modernization Act (FDAMA) and the Food and Drug Administration Amendments Act (FDAAA), the Sponsor of the trial is solely responsible for determining whether the trial and its results are subject to the requirements for submission to the Clinical Trials Data Bank, <http://www.clinicaltrials.gov>. Information posted will allow subjects to identify potentially appropriate trials for their disease conditions and pursue participation by calling a central contact number for further information on appropriate trial locations and trial site contact information.

